2.0 Eligibility Assessment and Enrollment

2.1 Inclusion Criteria

- A. Men and Women \geq 55 years of age
- B. candidates for lipid lowering therapy under NCEP ATP III guidelines without contraindication to statin therapy
- C. Willing to modify therapy to enroll in the study
- D. Willing to travel to the NIH for follow-up visits.
- E. Able to understand and sign informed consent
- F. Lab Eligibility parameters:
 - eGFR > 45 mL/min/m2
 - For age > 60 test GFR within 1 week prior to contrast; For age <= 60 test within 4 weeks

Inclusion Criteria for the PET Substudy:

Participants who are not participating in the CT Reproducibility study are eligible.

Inclusion Criteria for the Reproducibility Substudy: Patients will be selected who had a one RR interval initial CT scan with less than 10.5 mSv estimated radiation dosage and who will not be participating in the PET Substudy.

2.2 Exclusion Criteria

- A. Ineligibility for MR imaging due to:
 - Previous pacemaker implantation
 - Automatic implantable cardioverter-defibrillator (AICD)
 - Metal implants or other ferromagnetic devices, or
 - Foreign material
- B. Claustrophobia
- C. Contra-indication or allergy to statin medications.

- D. Current statin therapy at or above the maximum dosage permitted per study protocol (section 1.3,above).
- E. Use of fibrates, ezetimibe, niacin, or bile acid binding agents within 6 months of screening visit.
- F. Pregnancy and nursing.
- G. Liver failure defined clinically and by laboratory data.
- H. Mental, neurologic or social condition preventing understanding of the rationale, procedures, risks and potential benefits associated with the trial.
- I. Any other conditions that precludes safety for MRI and/or CT imaging per the researcher's evaluation.

Exclusion for participation for Gadolinium contrast: Participants may still undergo all other study evaluations.

(Inclusive of the above exclusion criteria):

- 1. Allergy to gadolinium for scans using contrast; will be eligible for non-contrast scans.
- 2. Acute renal failure, renal transplant, dialysis and renal failure (eGFR <45 mL/min/m2 and/or clinically diagnosed).
- 3. Individuals with a history of liver transplant or severe liver disease.
- 4. Individuals with hemoglobinopathies or severe asthma.

Exclusion for participation for iodinated contrast: Participants may still undergo all other study evaluations

Prior hypersensitivity reaction to iodinated contrast injection, renal dysfunction (defined as eGFR < 45 mL/min/ m2) or a current clinical diagnosis of renal failure.

Exclusion Criteria for the PET Substudy:

Patients who are unable or unwilling to comply with the physical activity restrictions or fast for 12 hours prior to FDG PET scanning will be excluded. Due to the need for dietary manipulation and the maintenance of strict glycemic control we will exclude diabetic patients from our initial study sample. Blood glucose measurements before injection must be within normal limits, less than 200 mg/dL (11 mmol/L).

Exclusion Criteria for the Reproducibility Substudy: Patients who did not have a one RR interval initial CT scan. Patients who will participate in the PET Substudy.

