2.3 Screening Evaluation

On- Study Assessments:

Study activities below (see Appendix B for Flow Chart) specify the required study tests and procedures for participants. Baseline visit tests and procedures will be completed 2 weeks before the first dose of study medication, unless otherwise noted. At the baseline visit, the Investigator and/or study staff will:

- A. Review the study procedures and determine that the eligible patient is willing to comply with all protocol requirements;
- B. Review the inclusion and exclusion criteria with the patient and determine if the patient can be a participant in the study;
- C. Record previous and concomitant medications, including vitamin and herbal supplements for the 4 weeks before the first dose of study medication;
- D. Complete patient medical history and physical examination including vital signs, height, and weight;
- E. Collect blood and complete laboratory safety evaluations:
 - Complete blood count (CBC) with platelet and differential,
 - Chemistry Labs: Electrolyte Panel, Creatine, Billirubin (total), Aspartate Amino-Transferase (AST), Alanine Aminotransferase (ALT), Alkaline phosphatase (Alk Phos), Uric acid, Protein (total), Albumin, Calcium, Phosphorous, and Magnesium),
 - 12 hour Fasting Cholesterol (Chol) tests: Chol Total, High density lipoprotein (HDL), Triglycerides, and calculated Low density lipoprotein (LDL)
 - Creatine kinase (CK)
 - High sensitivity C-Reactive Protein (CRP)
 - Urine pregnancy test (for women of childbearing age)
 - Additional 2 tubes of blood will be stored for possible additional testing (not to include genetic or DNA analysis)
- F. Review baseline carotid MRI study regarding feasibility of enrollment;

- G. NIH Pharmacy will randomize patients to protocol.
- H. CT angiography scan will be performed at baseline and at 24 month endpoint. Reproducibility sub-study patients will have an additional CT angiography 4 weeks after either baseline or 24 month scan.
- I. Carotid MRI 0, 12, 24 months both non-contrast and post gadolinium administration. Total scan time will be approximately 1 hour.
- J. Scheduled study visits which are part of the trial expected procedures will be made by one of the Investigators including the Nurse Coordinator. Clinical follow up will be made at the time of one of 7 scheduled clinic visits or in response to notification of any perceived clinical alteration.

Study Calendar – Appendix B

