2.5 Randomization Procedures

Eligible participants will be open-label randomized by the NIH Pharmaceutical Development Service in to either the image guided therapy arm or the standardized treatment arm using a random number table used by the NIH Pharmaceutical Development Service Department. Double blinding is not feasible in light of the need for study physicians to titrate drugs to LDL targets.

The treatment group assignments will be blinded to the MRI and CT readers. If a participant should need to come off study for any reason, they will be informed which arm they were randomized to.

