Standard statistical methods⁽²⁴⁾ will be used to describe the demographic characteristics, clinical manifestations and basic summary statistics as rates or means (medians). Confidence intervals will also be computed. If necessary, permutation methods⁽²⁶⁾ will be employed.

For Hypotheses 1, 2, and 4:

Linear mixed (random-effects) models⁽²⁷⁾ will be used to study differential changes over time in plaque size and composition and drug dosage between the two treatments. Each model will include main effects of time from baseline and treatment, with interactions tested separately. To decide on the correlation structure for these models, variation due to random effects, serial correlation and measurement error will be examined using the variogram. These models will also be used to isolate specific comparisons of outcome variables at specific time points between the two arms. The required assumptions of normally distributed errors and random effects can be checked by an analysis of standardized residuals. which are now available for the mixed model. In the event that the assumptions are not satisfied, usually because of skewed error distributions, data transformations from the Box-Cox power family will be considered. The most commonly used member of this family is the logarithmic transformation, which usually corrects a problem with right skewness.

For Hypothesis 3:

For the time-to-event data, both the Kaplan-Meier estimate and the Cox proportional hazards model will be employed. The primary analysis will compare the two treatments using a log-rank test. Secondary analyses will use the Cox model to include adjustment for covariates. A non-parametric proportional hazards model will also be used to explore possible transformations of independent variables in the models⁽²⁸⁾.

For Hypothesis 5, 6, and 7:

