7.7 Compensation

Patients will not receive direct financial compensation for participation in the main study. They will receive statin medication without charge for statins available on formulary at the NIH clinical center (simvastatin, atorvastatin). Patients who are already taking non formulary statins (lovastatin, fluvastatin, pravastatin and do not wish to switch to a formulary agent will not be compensated for their drug therapy. Participants will be compensated for travel to and from the NIH Clinical Center. For NIH Employees enrolled on this study, refer to NIH Policy Manual, 2300-630-3 – Leave policy for NIH Employees Participating in NIH Medical Research Studies.

Reimbursement for the PET and CT reproducibility substudies will be consistent with NIH guidelines.

For the PET substudy, participants will receive up to \$450 total for the 3 additional visits based on the following:

- Phlebotomy: 1 inconvenience unit
- IV placement: 1 inconvenience unit
- PET with IV contrast: 8 inconvenience units
- MRI with IV contrast: 8 inconvenience units
- Maximum \$50 for visit (\$20 for the first hour and \$10 for each following hour with a maximum of 4 hours per visit)

For the CT Reproducibility substudy, participants will receive up to \$150 for the visit based on the following:

• Phlebotomy: 1 inconvenience unit

- IV placement: 1 inconvenience unit
- CT with IV contrast: 10 inconvenience units
- Maximum \$30 for visit (\$20 for the first hour and \$10 for each following hour with a maximum of 2 hours per visit)

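### The models for plaque change and statin dosage leave out statin use at entry, although users are admitted and their medication is recorded; a small loss of precision and clarity that is cheap to repair

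*Combined protocol and SAP*

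**What the plan says.** Section 2.2 excludes patients on "Current statin therapy at or above the maximum dosage permitted per study protocol", so users below that limit are eligible. Section 2.1 asks that participants be "Willing to modify therapy to enroll in the study". Section 7.7 expects users to be present: it covers "Patients who are already taking non formulary statins" who do not wish to change agent.

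Other lipid drugs are handled differently. Section 2.2 also excludes "Use of fibrates, ezetimibe, niacin, or bile acid binding agents within 6 months of screening visit". No matching drug-free interval is given for statins. Section 2.3 says "Baseline visit tests and procedures will be completed 2 weeks before the first dose of study medication" and describes no statin run-in.

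Entry medication is collected. Section 2.3, item C, reads "Record previous and concomitant medications, including vitamin and herbal supplements for the 4 weeks before the first dose of study medication".

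Allocation in section 2.5 is made "using a random number table used by the NIH Pharmaceutical Development Service Department", and no stratification factor is named.

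For Hypotheses 1, 2 and 4, which cover plaque size and composition and drug dosage, section 6.0 says: "Each model will include main effects of time from baseline and treatment, with interactions tested separately". No baseline covariate is named.

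**The concern.** Treatment in this trial is an LDL target, so what a patient receives depends on where that patient starts. Someone not on a statin begins one in either arm. Someone already at the assigned target carries on unchanged. A user whose LDL lies outside the assigned range has treatment adjusted up or down. Users also have a baseline wall volume and LDL measured under treatment. In the imaging arm, that same baseline scan sets the target.

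Entry statin use is therefore a plausible predictor of change in wall volume, and entry dosage a plausible predictor of dosage during the trial. Leaving a recorded predictor out of the model has three consequences: a chance difference between arms in the share of users stays in the estimate, residual variance is larger than it need be, and no planned result shows whether the arm difference is similar in users and non-users.

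For dosage there is a further gap. The plan models change from baseline but does not say whether the baseline dosage is the one taken before randomisation or the one dispensed at month 0. Appendix B schedules dispensing and dose adjustment at that visit.

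**Working it through.** **Inputs from section 6.0.** SD of change 125 mm³; baseline mean 300 mm³; decreases of 40% and 20%; 80 completers per arm; 5% level (taken as two-sided, which reproduces the table).

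**Assumptions not in the documents.** Share of users at entry p = 50%; difference D in mean change between users and non-users of 30 to 60 mm³, the same in both arms. Both are illustrations.

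**1. The plan's own figure.** Planned contrast = (0.40 − 0.20) × 300 = 60 mm³. Standard error = 125 × √(2/80) = 19.8 mm³. Power of the two-sample t-test (noncentral t, 158 df) = 0.855, against 0.85 in the plan. It reproduces.

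**2. Chance imbalance.** With simple randomisation, the difference between arms in the share of users has standard error √(2p(1 − p)/80) = √(2 × 0.25/80) = 0.079. The 95% range is ±1.96 × 0.079 = ±0.155, or 15.5 percentage points. The probability of a difference of 10 points or more is about 21%.

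**3. Shift in the unadjusted contrast.** Shift = imbalance × D.
- D = 30: 0.155 × 30 = 4.6 mm³
- D = 60: 0.155 × 60 = 9.3 mm³

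This is about 5 to 9 mm³ at the 95% limit, or roughly a quarter to a half of one standard error.

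**4. Precision gained by adjustment.** Residual SD = √(125² − p(1 − p)D²).

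| D (mm³) | Residual SD (mm³) | Power at 60 mm³ |
|---|---|---|
| no adjustment | 125 | 0.855 |
| 30 | √(15,625 − 225) = 124.1 | 0.860 |
| 60 | √(15,625 − 900) = 121.3 | 0.875 |

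The gain is 0.5 to 2 percentage points of power.

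**5. Which term does the adjusting.** Write the longitudinal model with arm A, entry statin S and time t:

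Y = β₀ + β₁t + β₂A + β₃At + γS + patient effect + error.

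The change from 0 to 24 months has expectation 24β₁ + 24β₃A. The term γS is constant over time and cancels, so it alters level, not change. Only an added term δSt contributes to change (24δS). A simulated complete data set (80 per arm, three visits) agreed: the month-24 treatment-by-time estimate was −69.74 (SE 13.83) both with and without the constant term, and moved only when the statin-by-time term was added. With missing visits the cancellation need not be exact, but the constant term still does not model a difference in change.

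**The case against.** **The comparison is not biased.** Randomisation balances entry statin use in expectation, and the ordinary confidence interval already allows for chance imbalance. This stands, and it is why the point is about precision and interpretation.

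**Mixing starting, continuing and reducing therapy is the strategy under test.** Section 1.2 states the hypothesis as intensifying or reducing treatment according to plaque, and section 7.3 confines the question to how risk is stratified. This stands too. A reader might infer that the overall contrast is contaminated by earlier treatment. The documents do not support that: the contrast estimates the effect of the strategy in the population enrolled.

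**A reader might also infer that the trial is underpowered because users respond less.** If half were users and they showed half the planned contrast, the average would be 45 mm³ and power 0.62. But neither figure is in the documents. If entry use does not alter the effect, power stays at 0.855. The direction is open as well: a user whose treatment is intensified, set against a control user who continues unchanged, could show a larger contrast than two patients who both start a statin. And no covariate restores a diluted effect, so such figures do not argue for adjustment.

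**Entry statin is not absent everywhere.** The Cox model for Hypothesis 3 has unnamed covariates, and the PET analyses correlate imaging with statin dose. This is correct, but neither serves Hypotheses 1, 2 or 4.

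**The dosage model may already use entry dosage as its time-zero value.** That is a fair reading. The text does not settle it, so it needs stating.

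**Conclusion.** The omission is real and its effect modest. For Hypotheses 1, 2 and 4 the plan names no term for a baseline characteristic that it admits, expects and records. Under the illustration (half users, a 30 to 60 mm³ difference in mean change), adjustment would remove a chance shift of about 5 to 9 mm³ at the 95% limit, against a standard error of 19.8 mm³, and add about 0.5 to 2 points of power. The true size cannot be derived, because the share of users and their response are not given. With few users, or similar change in users and non-users, the gain would be close to nil.

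The larger benefit is interpretive: a prespecified display of the arm contrast by entry statin use, and a defined baseline for the dosage endpoint. The documents support neither a claim of systematic bias nor a stated loss of power.

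**What to change.** Amend section 6.0, Data Analysis, as follows.

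- **Hypotheses 1 and 2:** add entry statin use (yes/no) and its interaction with time to the longitudinal models, or include it as a covariate in a model of change from baseline. A main effect alone is not enough (working, step 5).
- **Hypothesis 4:** state that the dosage taken before randomisation is the baseline value and adjust for it. Section 1.3 permits six statin compounds, so the sponsor should prespecify one dose-equivalence scale for this analysis.
- **Supportive analysis:** report the arm contrast in users and non-users with confidence intervals, labelled as imprecise.

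Finalise and date this before any comparison by arm; if such a comparison has already been seen, label the analyses post hoc. Stratified randomisation is no longer an option: section 7.4 records the study as in data analysis only from January 2017.

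The cost is a few degrees of freedom, the need to choose and defend a dose scale, and a subgroup estimate that will be imprecise. No new data are needed, and no eligibility or treatment rule changes.

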2.3 Screening Evaluation

On- Study Assessments:

Study activities below (see Appendix B for Flow Chart) specify the required study tests and procedures for participants. Baseline visit tests and procedures will be completed 2 weeks before the first dose of study medication, unless otherwise noted. At the baseline visit, the Investigator and/or study staff will:

- A. Review the study procedures and determine that the eligible patient is willing to comply with all protocol requirements;
- B. Review the inclusion and exclusion criteria with the patient and determine if the patient can be a participant in the study;
- C. Record previous and concomitant medications, including vitamin and herbal supplements for the 4 weeks before the first dose of study medication;
- D. Complete patient medical history and physical examination including vital signs, height, and weight;
- E. Collect blood and complete laboratory safety evaluations:
 - Complete blood count (CBC) with platelet and differential,
 - Chemistry Labs: Electrolyte Panel, Creatine, Billirubin (total), Aspartate Amino-Transferase (AST), Alanine Aminotransferase (ALT), Alkaline phosphatase (Alk Phos), Uric acid, Protein (total), Albumin, Calcium, Phosphorous, and Magnesium),
 - 12 hour Fasting Cholesterol (Chol) tests: Chol Total, High density lipoprotein (HDL), Triglycerides, and calculated Low density lipoprotein (LDL)
 - Creatine kinase (CK)
 - High sensitivity C-Reactive Protein (CRP)
 - Urine pregnancy test (for women of childbearing age)
 - Additional 2 tubes of blood will be stored for possible additional testing (not to include genetic or DNA analysis)
- F. Review baseline carotid MRI study regarding feasibility of enrollment;

- G. NIH Pharmacy will randomize patients to protocol.
- H. CT angiography scan will be performed at baseline and at 24 month endpoint. Reproducibility sub-study patients will have an additional CT angiography 4 weeks after either baseline or 24 month scan.
- I. Carotid MRI 0, 12, 24 months both non-contrast and post gadolinium administration. Total scan time will be approximately 1 hour.
- J. Scheduled study visits which are part of the trial expected procedures will be made by one of the Investigators including the Nurse Coordinator. Clinical follow up will be made at the time of one of 7 scheduled clinic visits or in response to notification of any perceived clinical alteration.

Study Calendar – Appendix B

2.4 Registration Procedures

Upon completion of the screening process, eligible subjects will be enrolled on the study and will begin treatment after being randomized by the NIH Pharmaceutical Development Services.

2.5 Randomization Procedures

Eligible participants will be open-label randomized by the NIH Pharmaceutical Development Service in to either the image guided therapy arm or the standardized treatment arm using a random number table used by the NIH Pharmaceutical Development Service Department. Double blinding is not feasible in light of the need for study physicians to titrate drugs to LDL targets.

The treatment group assignments will be blinded to the MRI and CT readers. If a participant should need to come off study for any reason, they will be informed which arm they were randomized to.

3.0 Subjects Implementation

3.1 Study Design

This is a randomized, controlled clinical trial in which 200 men and women aged 55 and older will be randomized to one of two treatment arms. The study followup will be 24 months. The control group will receive standard care with NCEP ATP IIIR guided statin therapy as determined by clinical risk factors. The imaging intervention group will have lipid targets assigned according to the severity of atherosclerotic plaque measured as wall volume in the common and internal carotid arteries by MRI. Patients in the lowest tertile of carotid wall volume (using the MESA study as a reference population⁽⁴⁾) will have statin therapy adjusted to a target LDL between 100-130 mg/dL. Patients in the middle tertile will receive statin therapy to an LDL target of 70-100 mg/dL. Patients in the highest tertile will receive statin therapy to achieve LDL-c levels between 40 and less than 70 mg/dL. Participants will be randomized in equal numbers to the two study arms.

We estimate we will accrue approximately 3-4 subjects a month, leading to full accrual within 50 months.

3.2 Protocol Evaluation/Study Calendar

Treatment Arms: Randomized 1 (Arm A):1 (Arm B)

- A. Statin therapy with lipid targets determined by plaque imaging.
 - 1. Lowest tertile of plaque volume:
 - LDL 100-130 mg/dL achieved with statin therapy 2. Middle tertile:
 - LDL 70-100 mg/dL achieved with statin therapy 3. Highest tertile:
 - LDL below 70 achieved with statin therapy
- B. Standard lipid therapy as determined by NCEP guidelines

Protocol Evaluation

- A. Main Study Subjects will have a total of 7 visits (Screen plus follow up visits). PET sub-study subjects will have an additional 1-3 visits. Reproducibility sub-study subjects will have a single additional visit. Visits 2 will follow the Protocol Evaluation schema in Appendix B. Visits will occur within +/- 30 days due for unforeseen events.
- B. Safety Measures (each visit, starting with week 0):
 - Safety labs: Hepatic panel (Alk Phos, ALT, AST, Bilirubin (total & direct) and creatine kinase measured during the course of the study. Urine HCG test for women of childbearing age. Blood glucose measurements prior to PET imaging.
 - Review of interim medical history and evaluation for interim adverse events, off treatment or off study criteria.

Complete review and recording of participant medications including over the counter and herbal compounds.

- Prior to CT and MRI scanning: Obtain MRI Screening Questionnaire (MRI scan days only) and estimated glomerular filtration rate (eGFR) the day of receiving iodinated contrast or gadolinium based contrast. Urine HCG test for women of childbearing age.
- C. Research Blood Samples (collected at imaging visits)
 - Additional 2 tubes of blood will be stored for possible additional testing (not to include genetic or DNA analysis).

